MECHANISMS OF WALKING RECOVERY AFTER STROKE (NCT02858349)

UNIVERSITY OF CINCINNATI IRB RESEARCH PROTOCOL 2016-1916

Most Recent IRB Approval: 2018-05-24

STUDY PROTOCOL AND STATISTICAL ANALYSIS PLAN

STUDY PROTOCOL

Research Design

[figure not shown]
This study will use a single-group repeated measures design. Ten subjects with chronic stroke will have clinical walking assessment and brain imaging before and after a 4 week control period and 4 weeks of locomotor high-intensity interval training (Figure 1). The control period will be used to confirm test-retest reliability of the measures and the absence of spontaneous improvements.^{1,2}

Recruitment. As in previous studies, we will recruit persons with stroke from the Greater Cincinnati Northern Kentucky area by collaborating with our large referral base of regional therapists, physicians and support groups and by using our existing database of >300 local persons with stroke who are interested in participating in research. Clinician referrals can be done in two ways: 1) the clinicians may provide our name and contact information to the potential subject; 2) if the potential subject verbally approves, the clinician can give us their name and contact information.

For persons interested in participating, we will further explain the study, confirm initial eligibility and perform informed consent. After a research staff member explains the purpose of study and the consent, potential participants will be given at least 24 hours to decide if they want to participate. During this consenting process, the subject will be provided a copy of the consent form. Standardized questions will be asked to ensure that the subject understands the study before consenting. The consent form also includes a HIPAA authorization.

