Eligibility Criteria. Based on our research experience, previous studies and American College of Sports Medicine (ACSM) guidelines,³ we will observe the following eligibility criteria. **Inclusion criteria:** 1) age 30-90 years; 2) unilateral stroke experienced >6 months prior to enrollment in middle cerebral artery (MCA) territory without complete disruption of the putamen on the lesion side;⁴ 3) walking speed ≤ 1.0 m/s on the 10 meter walk test;^{5,6} 4) able to walk 10m over ground with assistive devices as needed and no physical assistance.⁷ **Exclusion criteria:** 1) MRI incompatibility (e.g. metallic or electronic implants, severe claustrophobia); 2) inability to perform mental imagery (time dependent motor imagery screening test [TDMI]);^{8,9} 3) evidence of significant arrhythmia or myocardial ischemia on treadmill ECG stress test, or significant baseline ECG abnormalities that would make an exercise ECG uninterpretable;³ 4) recent (<3 months) cardiopulmonary hospitalization; 5) unable to communicate with investigators or correctly answer consent comprehension questions; 6) significant ataxia or neglect (score of 2 on NIH stroke scale item 7 or 11);¹⁰ 7) severe lower extremity (LE) spasticity (Ashworth >2);¹¹ 8) recent (<3 months) illicit drug or alcohol abuse or significant mental illness; 9) major post-stroke depression (PHQ-9 ≥ 10)¹² in the absence of management of the depression by a health care provider (either anti-depressant medication or psychotherapy); 10) participating in physical therapy or another interventional research study; 11) recent (<3 months) paretic LE botulinum toxin injection; 12) concurrent progressive neurologic disorder or other major medical, orthopedic or peripheral vascular conditions that would limit improvement; 13) pregnancy.

Screening. After informed consent, subjects will undergo a screen including: medical record review, a history and physical, a depression screen (PHQ-9),¹² stroke-specific testing of mental imagery ability (TDMI),^{8,9} aphasia screening (Western Aphasia Battery Screening Test¹³), a motor impairment assessment (Fugl-

Meyer¹⁴), a 10m walk test,^{5,15} a resting ECG, a treadmill screening test¹⁵ and a stroke-specific treadmill ECG stress test¹⁶ to confirm eligibility and to obtain baseline characteristics and potential cofactors.

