*The Global Rating of Change (GROC)*⁴⁰ is a questionnaire that assesses overall impressions of change in health status from the perspective of the participant. The GROC is a 15 point ordinal scale with -7 indicating "a very great deal worse," 0 indicating "no change," and +7 indicating "a very great deal better". The GROC is not applicable at baseline testing because it measures change only.

Brain Imaging Procedures

Like clinical outcomes, brain imaging will be performed before and after the 4-week control period and after the locomotor HIT intervention for subjects with stroke. All scans will be performed on a 3.0T MRI system in the Imaging Research Center at CCHMC. Each imaging session will involve approximately one hour of brain scanning. During scanning, subjects will be positioned in a custom scaffold to stabilize the body and control leg movement. Initial alignment scans will be performed, followed by high-resolution anatomical scans, diffusion scans, functional scans and perfusion scans. The functional scans will be focused on the assessment of brain activation during imagined walking,^{41,42} knee extension^{43,44} and cognitive tasks. These tasks may involve

presentation of visual or auditory stimuli and subjects may be asked to respond by performing an actual or imagined movement, a cognitive task or by button-press. Subjects will be monitored by camera during functional scanning for compliance. Subjects will also practice task conditions prior to brain imaging.

Adverse Event (AE) Monitoring

Each study visit, subject voluntary reporting of AEs will be encouraged and AEs of interest will be specifically queried for subjects with stroke, including: falls, orthopedic injuries, faintness, new/increased pain and muscle soreness. During clinical testing and training sessions, subjects will also have monitoring and post-session questioning to identify any signs or symptoms of cardiorespiratory insufficiency, new/worsening neurological impairments or orthopedic injury.

STATISTICAL ANALYSIS PLAN

Clinical Trial Hypotheses. From PRE-2 to POST, subjects will exhibit a significant increase in walking speed (primary hypothesis) and other outcomes (secondary hypotheses).

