Statistical Analysis. A mixed effects general linear model will be used with the outcome of interest (e.g. walking speed) as the dependent variable, a fixed (categorical) effect for time (PRE-1, PRE-2, POST) and an unstructured covariance matrix to account for repeated measures within the same participant. Hypotheses will be tested by the significance of the contrast estimate from PRE-2 to POST at the 0.05 significance level. PRE-1 and PRE-2 will also be compared to confirm test-retest reliability and the absence of spontaneous changes during the control period.

LITERATURE CITED

3. American College of Sports Medicine (ACSM). *ACSM's guidelines for exercise testing and prescription*. 9th ed. Philadelphia, PA: Lippincott Williams & Wilkins; 2014.
11. Ashworth B. Preliminary trial of carisoprodol in multiple sclerosis. *Practitioner*. 1964;192:540-542.

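### A PRE-1 to PRE-2 comparison in ten people, with no stated criterion, will usually not show that spontaneous change is absent; report its estimate and 95% CI, and set the HIT-period change beside the control-period change

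*Combined protocol and SAP*

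**What the plan says.** The protocol's Research Design section states: "This study will use a single-group repeated measures design". On size and schedule it says: "Ten subjects with chronic stroke will have clinical walking assessment and brain imaging before and after a 4 week control period". It gives the control period two jobs: "The control period will be used to confirm test-retest reliability of the measures and the absence of spontaneous improvements".

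In the SAP, the Clinical Trial Hypotheses paragraph reads: "From PRE-2 to POST, subjects will exhibit a significant increase in walking speed (primary hypothesis) and other outcomes (secondary hypotheses". The Statistical Analysis paragraph specifies a mixed model with "a fixed (categorical) effect for time (PRE-1, PRE-2, POST) and an unstructured covariance matrix", and continues: "Hypotheses will be tested by the significance of the contrast estimate from PRE-2 to POST at the 0.05 significance level". The control period is covered by one sentence: "PRE-1 and PRE-2 will also be compared to confirm test-retest reliability and the absence of spontaneous changes during the control period".

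The documents give no margin, decision rule or confidence interval for the PRE-1 to PRE-2 comparison. They also give no SD of change, expected drift, power or dropout rate. The 0.05 level is attached to PRE-2 to POST only.

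**The concern.** The control period is the trial's only comparator. Its planned use is to confirm that nothing changes without training, but the plan does not say what result would count as confirmation. In ten people a moderate drift could easily go undetected. If the result were then reported as showing no spontaneous change, readers could credit the whole PRE-2 to POST gain to HIT when part of it might be drift or practice.

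The model contains what is needed to compare the two periods directly, but no such contrast is planned. With complete data PRE-1 does not enter the PRE-2 to POST estimate at all, so the control period informs the interpretation only through the separate PRE-1 to PRE-2 comparison.

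**Working it through.** **Inputs.** From the documents: n = 10, three visits, time as a category with unstructured covariance, alpha 0.05. Assumed, because the documents do not say: two-sided testing and complete data. Results are in units of the SD of the 4-week change, which is not given; for m/s an assumed range of 0.05 to 0.20 is used. The plan has no power or precision figure to reproduce.

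**1. Precision.** With complete data and unstructured covariance, each pairwise contrast equals the mean paired difference, here taken on 9 df. Half-width = t(0.975, 9) × SD/√n = 2.262 × SD/√10 = 0.715 SD.
- SD 0.05 m/s: ± 0.036 m/s
- SD 0.10 m/s: ± 0.072 m/s
- SD 0.20 m/s: ± 0.143 m/s

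If only 8 people had both visits (an assumption), the half-width would be 0.84 SD.

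**2. Power of PRE-1 vs PRE-2** (noncentral t, noncentrality d√10):
- drift d = 0.3 SD: 14%
- d = 0.5 SD: 29%
- d = 0.8 SD: 62%
- d = 1.0 SD: 80%

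A drift of 0.5 SD would thus be missed in about 71% of trials (100 − 29).

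**3. What the interval can exclude when there is no true drift.** The chance that the upper 95% limit lies below +0.5, +0.8 and +1.0 SD is 29%, 62% and 80%. Two one-sided 5% equivalence tests would succeed in about 7%, 52% and 79% of trials at margins of 0.5, 0.8 and 1.0 SD.

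**4. False attribution, as illustration only.** Suppose that non-significance is read as confirmation, HIT has no effect, and drift is 0.5 control-change SD in both periods. By simulation, the pattern of a non-significant control period with a significant HIT-period gain occurs as follows (correlation of the two changes from +0.5 to −0.5):
- equal SDs of the two changes: 15–25%
- HIT-change SD 1.5 times larger: 7–14%
- HIT-change SD 2 times larger: 4–9%

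With equal SDs, PRE-2 to POST alone would be falsely positive in 29%, so the planned control check does give some protection. If that drift stopped after the control period, or there were none, the pattern would occur in about 1–2% (equal SDs).

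**5. The contrast of changes,** (POST − PRE-2) − (PRE-2 − PRE-1). With equal SDs its SD is SD_change × √(2 − 2r), where r is the correlation of the two changes. They share PRE-2 with opposite sign, so measurement error pushes r negative.
- r = 0: factor 1.414, half-width 0.715 × 1.414 = 1.01 SD, power for a 1.0 SD HIT effect 51%
- r = −0.5: factor 1.732, half-width 0.715 × 1.732 = 1.24 SD, power 37%

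PRE-2 to POST has 80% power for the same 1.0 SD effect. If drift of 0.5 SD stops after the control period and HIT has no effect, the contrast is significantly negative in 13% of trials at r = −0.5, 17% at r = 0 and 29% at r = +0.5.

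**The case against.** The strongest reply has four parts.

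First, ten people are not bound to fail. A reader might infer that no criterion could ever let this comparison show absence of drift. That does not follow: step 3 shows that a margin near 1 SD would be met in about 80% of trials with no true drift. If the SD of change is small, 1 SD is also a small speed: at an assumed 0.05 m/s the half-width is only 0.036 m/s. This stands. The supportable statement is that the data will usually not exclude 0.5 SD, and that no criterion has been set.

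Second, a reader might infer that the plan treats a non-significant result as proof of no change. It does not say so. The natural reading is a model contrast, which comes with an estimate and standard error. This also stands, but the plan does not commit to reporting the interval, and the word confirm has no defined meaning without a criterion.

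Third, the eligibility criteria reduce the risk of drift. Stroke must be more than 6 months old, exclusions include "participating in physical therapy or another interventional research study; 11) recent (<3 months) paretic LE botulinum toxin injection", and walking and treadmill tests at screening give some practice before PRE-1. These make large, equal drift in both periods less likely. They do not turn a ten-person comparison into confirmation, and the protocol itself thought drift worth checking.

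Fourth, the added contrast is imprecise and can mislead if drift is not constant. This stands, and it limits the contrast to descriptive use.

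**Conclusion.** The concern holds in a limited form. The plan asks a ten-person comparison to confirm absence of spontaneous change without a criterion, and does not set the two periods' changes against each other. The precision and power figures follow from n = 10 under complete data and two-sided testing. Whether 0.72 SD matters in practice depends on an SD of change that the documents do not give. The false-attribution percentages rest on assumed drift, correlation and SD ratio, and on a reading of non-significance that the plan does not state; they show a mechanism, not an expected rate.

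A reader might also infer that the primary analysis is wrong. The documents do not support that: the PRE-2 to POST test is the one the hypothesis calls for. Nothing here bears on the test-retest reliability aim. This is a cheap improvement in what can be concluded, and worth making.

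**What to change.** Keep the primary test and the test-retest aim as they are, and make two changes.

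1. In the protocol's Research Design section and the SAP's Statistical Analysis paragraph, replace the aim of confirming absence of spontaneous change with: *estimate the PRE-1 to PRE-2 change with its 95% CI; a non-significant difference will not be taken as absence of change.*
2. From the same model, report (POST − PRE-2) − (PRE-2 − PRE-1) with its 95% CI as a secondary, descriptive estimate. It neither gates nor replaces the primary test, and need not be repeated at every statement that attributes improvement to HIT.

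No equivalence margin is proposed at this sample size.

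The cost is two reworded sentences and one extra estimate, with no new data and no change to the power of the primary test. The downsides are the contrast's wide interval and the false signal of harm it can give if drift stops after the control period (step 5 of the working). It removes only drift that is equal in both periods, and does not address attention or tester-expectation effects. The SAP should state these limits beside the estimate.
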